16. DATA HANDLING AND RECORD KEEPING

Training sessions, regular monitoring of Investigators by Sponsor-designated personnel, instruction manuals, data verification, crosschecking, and data audits will be performed to ensure quality of all study data. Investigator meetings may be performed to prepare Investigators and other study personnel for appropriate collection of study data.

The Sponsor will review and validate study data as defined in the monitoring plan.

It will be the responsibility of the Investigator to ensure that the essential documents are available at the study site. Any or all these documents may be subject to, and should be available for, monitoring by the Sponsor or inspection by the regulatory authorities as defined in the monitoring plan.

16.1. Direct Access to Source Data/Documentation

The Investigator agrees by his/her participation that the results of this study may be used for submission to national or international registration. If required, these authorities will be provided with the name of the Investigator and his or her address, qualifications, and extent of involvement. It is understood that the Investigator is required to provide Sponsor with all study data, complete reports, and access to all study records.

Data generated by this study must be available for inspection by any regulatory authorities, by the Sponsor and by the IRB/IEC as appropriate. At a subject's request, medical information may be given to his or her personal physician or other appropriate medical personnel responsible for his or her welfare. Medical information obtained from subjects during the course of this study is confidential and disclosure to third parties other than those noted above is prohibited.

16.2. Study Drug Accountability

All supplies of CD388 Injection/placebo required for completion of this study will be provided by the Sponsor. It is the responsibility of the unblinded Pharmacy or study staff to ensure that a current record of drug inventory and drug accountability is maintained. Inventory and accountability records must be readily available for inspection by the monitor and are open to inspection at any time by applicable regulatory authorities.

16.3. Retention of Records

Essential documents should be retained until at least 2 years after the last approval of a marketing application in an ICH region and until there are no pending or contemplated marketing applications in an ICH region or at least 2 years have elapsed since the formal discontinuation of clinical development of the investigational product and shipment and delivery of the drug for investigational use is discontinued. These documents should be retained for a longer period, however, if required by the applicable regulatory requirements of specific ICH and non-ICH countries, or by an agreement with the Sponsor. The Sponsor will inform the Investigator/institution as to when these documents no longer need to be retained.

16.4. Long-term Retention of Samples for Additional Future Research

Samples collected in this study may be stored for up to 15 years (or according to local regulations) for additional research. Samples will only be used for research related to influenza virus infection, flu-like disease, and safety, reactogenicity, and immunogenicity of CD388. They may also be used to develop tests/assays related to CD388 and influenza. The research may begin at any time during the study or the post-study storage period.

Stored samples will be coded throughout the sample storage and analysis process and will not be labeled with personal identifiers. Subjects may withdraw their consent for their samples to be stored for research.

17. FINANCING AND INSURANCE

The financing and insurance for this study are outlined in the Clinical Trial Agreement.

18. PUBLICATION POLICY

The data generated in this clinical study are the exclusive property of the Sponsor and are confidential. Authorship on any publication of the results from this study will be based on contributions to study design, enrollment, data analysis, and interpretation of results.

20. APPENDICES

APPENDIX 1. ACCEPTABLE METHODS OF CONTRACEPTION

An acceptable method of contraception includes one of the following:

- Abstinence from heterosexual intercourse
- Hormonal contraceptives (birth control pills, injectable/implant/insertable hormonal birth control products, transdermal patch)
- Intrauterine device (with or without hormones)
- A double barrier method (e.g., condom and spermicide)

APPENDIX 2. ECG AND VITAL SIGN ABNORMALITIES

Important abnormalities from the ECG readings are summarized below:

	ECG Parameter			
Abnormality	HR	PR	QRS	QTcF
Abnormalities on actual values				
Abnormally low	<45 bpm	NA	-	-
Abnormally high	≥120 bpm	>220 msec	≥120 msec	-
Borderline prolonged QT (males)	-	-	-	450 msec to ≤480 msec
Borderline prolonged QT (females)				470 msec to ≤480 msec
Prolonged QT	-	-	-	481 msec to ≤500 msec
Pathologically prolonged QT	-	-	-	>500 msec
Abnormalities on changes from bas	Abnormalities on changes from baseline			
Normal QTcF change	-	-	-	<30 msec
Borderline QTcF change	-	-	-	30 msec to ≤60 msec
Abnormally high QTcF change	-	-	-	>60 msec

Abbreviations: bpm = beats per minute; HR = heart rate; NA = not applicable; PR = PR interval; QRS = QRS interval; QTcF = QT interval corrected for heart rate using Fridericia's formula.

Important abnormalities for vital signs are summarized below:

		Vital Signs Parameter		
Abnormality	HR	DBP	SBP	
Abnormally low	≤45 bpm	≤50 mmHg	≤90 mmHg	
Grade 1 or mild	-	>90 mmHg to <100 mmHg	>140 mmHg to <160 mmHg	
Grade 2 or moderate	-	≥100 mmHg to <110 mmHg	≥160 mmHg to <180 mmHg	
Grade 3 or severe	-	≥110 mmHg	≥180 mmHg	
Abnormally high	≥120 bpm	-	-	

Abbreviations: DBP = diastolic blood pressure; HR = heart rate; SBP = systolic blood pressure.

	Grade 1	Grade 2	Grade 3	Grade 4
Fever ^a	38.0 to <38.6°C	≥38.6 to <39.3°C	≥39.3 to <40.0°C	≥40.0°C
	(100.4 to <101.5°F)	(≥101.5 to <102.7°F)	(≥102.7 to <104.0°F)	(≥104.0°F)

a. Non-axillary temperatures only.

For tachypnea and hypoxia, refer to the grading scale in Table 7.

APPENDIX 3. DIAGNOSTIC CRITERIA AND MANAGEMENT FOR ANAPHYLAXIS

Diagnostic Criteria for Anaphylaxis

Anaphylaxis is highly likely when any one of the following 3 criteria are fulfilled:

1. Acute onset of an illness (minutes to several hours) with involvement of the skin, mucosal tissue, or both (e.g., generalized hives, pruritus or flushing, swollen lips, -tongue, -uvula)

and at least one of the following:

- a. Respiratory compromise (e.g., dyspnea, wheeze-bronchospasm, stridor, reduced peak expiratory flow, hypoxemia)
- b. Reduced blood pressure or associated symptoms of end-organ dysfunction (e.g., hypotonia [collapse], syncope, incontinence)
- 2. Two or more of the following that occur rapidly after exposure to a likely allergen for that subject (minutes to several hours):
 - a. Involvement of the skin-mucosal tissue (e.g., generalized hives, itch-flush, swollen lips-tongue-uvula)
 - b. Respiratory compromise (e.g., dyspnea, wheeze-bronchospasm, stridor, reduced peak expiratory flow, hypoxemia)
 - c. Reduced blood pressure or associated symptoms (e.g., hypotonia [collapse], syncope, incontinence)
 - d. Persistent gastrointestinal symptoms (e.g., crampy abdominal pain, vomiting)
- 3. Reduced blood pressure after exposure to known allergen for that subject (minutes to several hours):
 - a. Systolic blood pressure <90 mmHg or >30% decrease from that person's baseline

Management of Anaphylaxis

- 1. **Epinephrine:** When a subject meets any of the diagnostic criteria, the subject should receive epinephrine immediately, as it is the treatment of choice in anaphylaxis. Aqueous epinephrine, 0.01 mg/kg (maximum dose, 0.5 mg) administered intramuscularly every 5 to 15 minutes as necessary, is the recommended dosage for controlling symptoms and maintaining blood pressure. The 5-minute interval between injections can be liberalized to permit more frequent injections if deemed necessary by the clinician.
- 2. Oxygen and adrenergic agonists: High-flow oxygen (through a nonrebreather mask or endotracheal tube) should be administered to subjects experiencing respiratory symptoms or hypoxemia. Those who are hemodynamically unstable might benefit from oxygen as well. Inhaled β_2 -agonists, such as albuterol, might be useful for bronchospasm refractory to epinephrine.

- 3. **Positioning of the subject:** Subjects in anaphylactic shock (i.e., those with anaphylaxis and signs of critical organ hypoperfusion) should be placed in a recumbent position with the lower extremities elevated unless precluded by shortness of breath or vomiting.
- 4. **Fluid resuscitation:** Subjects who remain hypotensive despite epinephrine should have aggressive fluid resuscitation. Large volumes of crystalloid might be needed in the first 5 to 10 minutes; in severe reactions with hypotension, up to 35% of the blood volume might extravasate in the first 10 minutes, and vasodilatation can cause pooling, with even more reduction in the effective blood volume and thus distributive shock.
- 5. **Vasopressors:** Potent vasopressors, such as noradrenaline, vasopressin, or metaraminol, might be required to overcome vasodilatation if epinephrine and fluid resuscitation have failed to maintain a systolic blood pressure of greater than 90 mmHg.
- 6. **H₁- and H₂-antihistamines:** Antihistamines (H₁- and H₂-antagonists) are slower in onset of action than epinephrine, have little effect on blood pressure, and should be considered a second-line treatment for anaphylaxis.
- 7. **Corticosteroids:** Because the onset of action is slow, steroids are not useful in the acute management stage. It has been suggested that their use might prevent a protracted or biphasic reaction.
- 8. Glucagon for persistent hypotension in subjects taking β-blocker: Theoretically, there are multiple mechanisms by which β-blockade could blunt the response to epinephrine. If administration of epinephrine in these subjects is ineffective, administration of glucagon can be attempted. Glucagon is thought to reverse refractory hypotension and bronchospasm by activating adenylate cyclase independent of the β-receptor; however, the occurrence and importance of this mechanism of action in anaphylaxis is unproved.
- 9. **Observation:** After the treatment of an anaphylactic reaction, an observation period should be considered for all subjects as the reaction might recur as the effect of epinephrine wears off (intramuscular epinephrine results in increased serum levels for an hour or more) and because of the risk of a biphasic reaction (1–72 hours after the acute reaction).

Source: Sampson 2006.

APPENDIX 4. RASH MANAGEMENT

For subjects reporting rash, the following should be performed:

All rashes will be discussed between the Investigator and the Sponsor, and in case of a causal relationship between the rash and the study drug, then the following visits and assessments will be performed as indicated below and in the "Visit Schedule for Rash Management" (see Appendix 5). Unscheduled follow-up visits for close follow-up of rash will be performed based on the grade (severity) of the rash. At the Investigator's discretion, additional visits and assessments may be performed.

The rash event should be captured in the AE section of the electronic case report form (eCRF), as well as in more detail in the specific rash assessment pages of the eCRF.

In case of rash, blood samples need to be collected for safety laboratory testing, and processed by the local laboratory. These samples need to be collected during the unscheduled visits as described below and in Appendix 5. A copy of the local laboratory reports should be anonymized and will be retrieved by the monitor.

The following parameters need to be tested: aspartate aminotransferase (AST), alanine aminotransferase (ALT), creatinine, erythrocyte sedimentation rate, and a complete blood cell count (including hemoglobin, hematocrit, red blood cell [RBC] count, white blood cell [WBC] count, neutrophils, lymphocytes, monocytes, eosinophils, basophils, and platelet count).

Digital pictures need to be taken as described below and in Appendix 5. Digital pictures will be anonymized and stored on the Sponsor's secure server. Only the study team will have access to the pictures.

The subject may be treated symptomatically until the rash resolves. If the rash is considered to be most likely due to concomitant illness or non-study medication, standard management, including discontinuation of the likely causative agent, should be undertaken, and the continuation of the subject in the study should be discussed with the Sponsor.

Dermatologist fees for evaluating subjects who experience a rash will be reimbursed by the Sponsor.

The following grades are based on the DAIDS Toxicity Grading Scale (DAIDS 2017) with adaptations made by the Sponsor:

Subjects should be informed that they should contact their doctor and visit the clinic immediately (unscheduled visit, day 1 of the rash) when they notice any rash.

Grade 1 Rash

A Grade 1 rash is defined as **erythema**.

- Subjects may continue the intake of study drug(s) (at the Investigator's discretion).
- An unscheduled visit for initial rash evaluation (day 1 of the rash) is required.
- Assessment of safety blood samples by the local laboratory is required. A copy of the local laboratory report should be anonymized and will be retrieved by the monitor.

- Digital pictures should be taken within 24 hours after the onset of the rash.
- Referral to a dermatologist is only needed if the rash diagnosis is uncertain (preferably within 24 hours after the onset of the rash). A copy of the dermatologist's report should be anonymized and will be retrieved by the monitor.
- Cetirizine, levocetirizine, topical corticosteroids, or antipruritic agents may be prescribed.
- The description of the rash should be reported per 'Unscheduled Visit in Case of Rash' in the eCRF (i.e., the initial rash assessment pages).

For close follow-up of the rash, unscheduled visits will also be performed 1 and 7 days after the initial assessment of the rash. At these visits, safety blood samples and digital pictures should be taken. The follow-up rash assessment pages of the eCRF should be completed for all follow-up visits. For these and all subsequent local laboratory blood sample assessments: a copy of the local laboratory reports should be anonymized and will be retrieved by the monitor.

If the rash is unresolved after 7 days, additional unscheduled visits may be performed at the Investigator's discretion. Upon resolution/stabilization of the rash, digital pictures should be taken and the final rash assessment pages of the eCRF should be completed.

The subject should be advised to contact the Investigator immediately if there is any worsening of the rash, if any systemic signs or symptoms appear, or if mucosal involvement develops.

In case the rash evolves from a Grade 1 to a higher grade, additional unscheduled visits have to be conducted according to the guidelines for Grade 2 or Grade 3–4 rash, respectively.

Grade 2 Rash

A Grade 2 rash is defined as **diffuse**, maculopapular rash **OR** dry desquamation.

• Subjects will permanently discontinue the intake of study drugs and be withdrawn from the study. No rechallenge is allowed.

Note: Subjects experiencing Grade 2 rash following the last intake of study drug may continue in the study as long as they are not re-exposed to suspect study drug.

- An unscheduled visit for initial rash evaluation (day 1 of the rash) is required.
- Assessment of safety blood samples by the local laboratory is required. A copy of the local laboratory report should be anonymized and will be retrieved by the monitor.
- Digital pictures should be taken within 24 hours after the onset of the rash.
- Referral to a dermatologist is required, preferably within 24 hours after the onset of the rash. A copy of the dermatologist's report should be anonymized and will be retrieved by the monitor.
- A biopsy is performed (preferably within 24 hours after the onset of the rash) if advised by the dermatologist. A copy of the biopsy report should be anonymized and will be retrieved by the monitor.
- Cetirizine, levocetirizine, topical corticosteroids, or antipruritic agents may be prescribed.

• The description of the rash should be reported per 'Unscheduled Visit in Case of Rash' in the eCRF (i.e., the initial rash assessment pages).

For close follow-up of the rash, unscheduled visits will also be performed 1 and 7 days after the initial assessment of the rash. At these visits, safety blood samples and digital pictures should be taken. The follow-up rash assessment pages of the eCRF should be completed for all follow-up visits. For these and all subsequent local laboratory blood sample assessments: a copy of the local laboratory reports should be anonymized and will be retrieved by the monitor.

If the rash is unresolved after 7 days:

- And there is an increase in AST/ALT of 1 or 2 times the baseline value OR an increase in AST/ALT of less than 5 times the upper limit of normal (ULN), subjects should be followed weekly with repeated local lab assessments and digital pictures until resolution of the AST/ALT abnormalities.
- And there is no increase in AST/ALT, additional unscheduled visits (including local lab assessments and digital pictures) may be performed at the Investigator's discretion.

Upon resolution/stabilization of the rash, digital pictures should be taken and the final rash assessment pages of the eCRF should be completed.

The subject should be advised to contact the Investigator immediately if the rash fails to resolve (after more than 2 weeks), if there is any worsening of the rash, if any systemic signs or allergic symptoms develop, or if mucosal involvement develops.

In case the rash evolves from a Grade 2 to a Grade 3–4 rash, additional unscheduled visits must be conducted according to the guidelines for Grade 3–4 rash.

Grade 3 or Grade 4 Rash

A Grade 3 rash is defined as:

- vesiculation, moist desquamation, or ulceration OR
- cutaneous event with one of the following (revised by the Sponsor):
 - elevations in AST/ALT more than $2\times$ baseline value and $\geq 5\times$ ULN
 - fever >38°C or 100°F
 - eosinophils >1000/mm³
 - serum sickness-like reaction

A Grade 4 rash is defined as:

- exfoliative dermatitis OR
- a generalized rash with mucous membrane involvement OR
- erythema multiforme OR
- Stevens-Johnson Syndrome OR
- rash associated with necrosis requiring surgery

- Subjects will **permanently discontinue** the intake of all study drug(s) and be withdrawn from the study with Grade 3 or 4 rash identified. No rechallenge is allowed.
- An unscheduled visit for initial rash evaluation (day 1 of the rash) is required.
- Assessment of safety blood samples by the local laboratory is required on the day of initial
 rash evaluation and the day thereafter (days 1 and 2 of the rash), and as indicated below.
 A copy of the local laboratory report should be anonymized and will be retrieved by the
 monitor.
- Digital pictures should be taken within 24 hours after the onset of the rash and on day 1 of the rash, and as indicated below.
- Referral to a dermatologist is required, preferably within 24 hours after the onset of the rash. A copy of the dermatologist's report should be anonymized and will be retrieved by the monitor.
- A biopsy should be performed within 24 hours after the onset of the rash. A copy of the biopsy report should be anonymized and will be retrieved by the monitor.
- Appropriate management should be undertaken and subjects should be followed until resolution of the rash.
- The description of the rash should be reported per 'Unscheduled Visit in Case of Rash' in the eCRF (i.e., the initial rash assessment pages). The follow-up rash assessment pages of the eCRF should be completed for all follow-up visits.

For close follow-up of the rash, unscheduled visits will be performed as follows:

- Follow-up visits on days 2, 3, and 4 of the rash are required. Additional safety blood samples and digital pictures are to be taken on these days only if the subject's AST/ALT on day 1 and/or day 2 of rash >2× baseline value, and/or ≥5 × ULN and/or in case of rash progression. For these and all subsequent local laboratory blood sample assessments: a copy of the local laboratory report should be anonymized and will be retrieved by the monitor.
- A follow-up visit on day 6 of the rash is required and additional safety blood samples and digital pictures are to be taken regardless of the day 1/2 AST/ALT levels or rash progression.
- Thereafter, weekly follow-up visits are required (or more frequently at the Investigator's discretion) as long as Grade 3–4 rash is present. Once Grade 3–4 rash has resolved to Grade ≤2, follow-up should be performed according to the instructions for follow-up visits for Grade 1 or Grade 2 rash, respectively.
- As long as the rash remains Grade 3 or 4, additional safety blood samples and digital pictures are required at these weekly follow-up visits only if the subject's AST/ALT on day 6 of rash is still >2× baseline value and/or ≥5 × ULN and/or in case of rash progression, until resolution or stabilization of the AST/ALT elevations.

Upon resolution/stabilization of the rash, digital pictures should be taken and the final rash assessment pages of the eCRF should be completed.

Subjects should be advised to contact the Investigator immediately if they notice any worsening of the rash.

A complete summary of the guidelines for rash management is given in Appendix 5.

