1.1. Schedule of Events

Table 1: Schedule of Events

	Screening		Clinica	al Resea	Clinical Research Unit (CRU) Inpatient Stay	(CRU) I	npatient	Stay			Outpa	Outpatient CRU Visits	tU Visit	20
Day (Window)	-28 to -2	-1	1	2	3–6	L	6	11	14	30 (±3)	45 (±3)	(5±)	90 (±7)	120/165 a (±14)
Informed consent	X													
Inclusion/Exclusion criteria	X	X												
Medical history/demographics	X													
Complete physical with vital signs (BP, RR, HR, oral temperature, height, weight, BMI)	X													
Targeted physical with vital signs (BP, RR, HR, oral temperature, weight ^b)		×	×°	×	X	X			×	X	X	×	×	×
Safety ECG ^d	X	X	X			X			×	X				X
Laboratory evaluations (CBC with platelets, coagulation, serum chemistry, lipids, urinalysis)	X	X		X	X e	X			X	X	X	X	X	×
Virology screening (HBV, HCV, HIV)	X													
Virology screening (SARS-CoV-2)		×												
Serum/urine pregnancy test f	X	X								X		×	X	X
FSH (if applicable to confirm postmenopausal status)	X													
Drug/alcohol screen 8	X	X												
Randomization			X											
Dosing of study drug			X											
Reactogenicity/injection site inspection h			X	X	X									
PK sample collection i			X	X	X	X	X	X	X	X	X	X	X	X
Pharmacogenomics blood sample ^j			predose											
Exploratory biomarker samples			predose		X e									
Anti-drug antibodies			predose						X	X	X	X	X	X
Nasopharyngeal swab collection ^k			predose	X	X	X	X	X	X	X				
Assess and record AEs ¹	→													↑
Concomitant medications/procedures review m	\													↑

[figure not shown]
research unit; DAR = drug-antibody ratio; ECG = electrocardiogram; FSH = folliele-stimulating hormone; HBV = hepatitis B virus; HCV = hepatitis C virus; HIV = human Abbreviations: AEs = adverse events; BMI = body mass index; BP = blood pressure, CBC = complete blood count; COVID-19 = coronavirus disease 2019; CRU = clinical immunodeficiency virus; HR = heart rate; hr = hour; ICF = informed consent form; PK = pharmacokinetic; RR = respiration rate; SARS-CoV-2 = severe acute respiratory syndrome coronavirus 2.

Schedule of Events (continued)

- The timing of this visit is Day 120 for Cohort 1 and Day 165 for Cohorts 2 and 3. For subjects who discontinue study early, the Day 120/165 procedures should be performed.
- b. Weight should be measured at each of the outpatient visits (Days 30, 45, 60, 90, 120/165).

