- On Day 1, the targeted physical examination should be performed predose. Vital signs collection will occur predose, 6 hours postdose, and as clinically indicated, and will be measured with the subject in a seated position for at least 3 minutes prior to measurement. ပ
- A triplicate 12-lead ECG is to be performed at screening, at CRU check-in on Day -1, predose (immediately prior to study drug administration) and 6 hours postdose (±10 minutes) on Day 1, and as indicated in the schedule. Subjects are to be resting (at least 5 minutes) and semi-recumbent when ECG is being conducted. d.
- Laboratory evaluations (including exploratory biomarker samples) need to be performed once during the Day 3-6 interval on Day 4. e.
- A sensitive serum pregnancy test (\(\beta\)-human chorionic gonadotropin) is required at screening and Day 120/165 for females of childbearing potential. Urine pregnancy test may be performed at all other time points. £.
- Drug and alcohol screen is to be performed during the outpatient visits if vital signs are abnormal (see Appendix 2). ьio
- and once approximately 8-12 hours postdose, then twice daily on other indicated study days at least 6 hours apart), with any abnormal findings reported as At indicated visits, inspection of administration site and surrounding area will be performed twice daily (once between approximately 2-4 hours postdose, AEs. Reactions will be rated according to the scale provided in Table 5. þ.
- Blood samples for PK analysis will be collected predose (-24 hour window); post-dose at 2, 4, and 12 hours (each ±10 minute window); 24 hours (±30 minute window); 48 hours (±1 hour window); 72, 96, 120 hours (each ±2 hour window); and in the morning on Days 7, 9, 11, 14. Postdose samples collected at outpatient CRU visits at Days 30, 45, 60, 90, and 120/165 have the same windows (i.e., in ±days) as the visits. . 🚅
- A mandatory pharmacogenomic (DNA) blood sample will be collected once, preferably on Day 1 (collection at another time point is allowed if necessary) to allow for pharmacogenomic research related to CD388. ..
- Nasopharyngeal swab samples will be collected predose on Day 1, and on Days 2, 5, 7, 9, 11, 14, and 30. 7
- Adverse events (including influenza-like illness which will be tested for both COVID-19 and flu) will be collected for all subjects from the time of signing the ICF through the final study visit.

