- e. Mean AUC_{0-3month} values (males and females combined) calculated over 3 months: rat by summing AUC from 3 doses and monkey by summing AUC from 2 doses, to cover a 3-month exposure period.
- f. Predicted human plasma PK for 50 mg starting dose (or 0.833 mg/kg based on a 60 kg person): $AUC_{0-\infty} = 3855 \ \mu g \times h/mL$. $C_{max} = 14.4 \ \mu g/mL$ (calculated from 5 mg/kg IV human PK as reported/projected in NC-CD388-05). Note: These exposures were predicted for IV administration and would represent the highest values expected as bioavailability from IM or SQ administration is anticipated to be approximately 70% of IV based on animal PK studies, potentially lowering the exposures in human from IM or SQ dosing.

Safety results of the ongoing clinical trial CD388.IM.SQ.1.01 have indicated no significant safety findings following single SQ administration of 50, 150 mg, and 450 mg CD388.

In summary, excellent safety margins were achieved with CD388 in 3-month toxicity studies relative to the FIH human dose conservatively scaled to BSA and to the predicted FIH plasma exposure. Although no adverse findings were identified in nonclinical studies, transient minor changes in clinical pathology parameters were observed in the absence of other changes, including no changes in cytokines and microscopic findings, and no CD388-related effects on kidney or the reticuloendothelial system. The outcome of the CD388 nonclinical safety program supports the proposed clinical program and dose of 50 mg, 150 mg, and 450 mg administered as bolus SQ injections. Results from the FIH study to date have shown no significant safety findings after 50 mg, 150 mg, and 450 mg CD388 administrations.

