6.5. Expected Duration of Subject Participation

A single dose of study drug will be administered SQ on Day 1. Study participation will require up to 28 days for screening procedures, and approximately 120/165 days for dosing and follow-up (check-in to the CRU on Day -1; CRU inpatient stay for study drug administration, observation, and assessments and procedures for 15 days [Days -1 to Day 14]; and 5 CRU outpatient visits for additional assessments and procedures).

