7.4. Subject Withdrawal Criteria

7.4.1. Withdrawal from Study Protocol

Subjects may withdraw consent to participate in this study at any time without penalty or loss of benefits to which the subject is otherwise entitled. Subjects who wish to withdraw completely from this clinical study should be encouraged to complete the Day 120/165 assessments. Every reasonable effort should be made to determine the reason a subject withdraws prematurely, and this information should be recorded on the appropriate page(s) of the electronic case report form (eCRF).

Subjects may be withdrawn from the study for any of the following reasons:

- Subject is unable or unwilling to continue
- Subject elects to withdraw informed consent
- Adverse event (whether or not related to study drug) that precludes further participation in the study in the judgment of an Investigator and/or Sponsor
- Protocol non-compliance
- Subject lost to follow-up, or follow-up is not possible
- The Investigator considers that it is in the subject's best interest not to continue participation in the study

If a subject is removed from the study for any reason, the subject will be followed for resolution of any ongoing AE(s).

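### Withdrawing Grade 3–4 rash subjects from a single-dose study avoids no exposure and ends their remaining scheduled PK, ADA and safety follow-up

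*Protocol*

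**What the plan says.** Section 6.5 of the protocol sets the dosing: "A single dose of study drug will be administered SQ on Day 1".

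For Grade 3 or 4 rash, Appendix 4 has subjects permanently stop study drug "and be withdrawn from the study with Grade 3 or 4 rash identified", and attaches no exception. For Grade 2 rash it also calls for discontinuation and withdrawal, but adds a Note: "Subjects experiencing Grade 2 rash following the last intake of study drug may continue in the study", provided they are not re-exposed.

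Some follow-up survives withdrawal:

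- Appendix 4, for Grade 3–4: "Appropriate management should be undertaken and subjects should be followed until resolution of the rash".
- Section 7.4.1: ongoing AEs are followed to resolution after removal for any reason.
- Table 1, footnote a: "For subjects who discontinue study early, the Day 120/165 procedures should be performed".

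Appendix 5, which Appendix 4 presents as the full summary of these rules, requires only drug discontinuation for Grade 3–4 rash. It does not mention withdrawal from the study.

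**The concern.** Stopping rules for rash serve to prevent further exposure. Here the whole dose has been given before any treatment-emergent rash can occur, so discontinuation and the ban on rechallenge are satisfied automatically. Withdrawal from the study then adds only the end of scheduled data collection.

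The result is also in the wrong order. In a single-dose trial the Grade 2 Note covers every post-dose Grade 2 rash, so the milder reaction keeps the full schedule and the more severe one loses it. Appendix 4 counts a serum sickness-like reaction as Grade 3. Later ADA titers and drug concentrations would help to interpret such an event.

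At stake are the secondary plasma PK endpoints (both AUC measures), the exploratory ADA endpoint and the primary safety follow-up, in the subjects whose data are most informative. Section 7.5 provides for replacement only of subjects withdrawn for reasons other than AEs.

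**Working it through.** The protocol gives no figure on this point to reproduce. The check counts scheduled samples and uses the protocol's PK prediction.

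**Scheduled post-dose samples (Table 1 and footnotes)**

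- PK: 2, 4, 12, 24, 48, 72, 96 and 120 h (8), plus Days 7, 9, 11 and 14 (4), plus Days 30, 45, 60, 90 and 120/165 (5). Total 8 + 4 + 5 = 17.
- ADA: Days 14, 30, 45, 60, 90 and 120/165. Total 6.

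**Samples still due at withdrawal.** The withdrawal day is an assumption, and that day's samples are taken as collected.

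| Withdrawal after | PK still due (of 17) | ADA still due (of 6) |
|---|---|---|
| Day 7 | 8 | 6 |
| Day 14 | 5 | 5 |
| Day 30 | 4 | 4 |
| Day 60 | 2 | 2 |

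In each row the early-discontinuation visit gives back at most one PK and one ADA sample.

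**Follow-up time.** Day 14 is 13 days after dosing. Withdrawal then removes (119 − 13)/119 = 89% of planned post-dose follow-up in Cohort 1, which ends on Day 120. In Cohorts 2 and 3, which end on Day 165, it removes (164 − 13)/164 = 92%.

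**Share of AUC after Day 14.** Table 2, footnote f (Section 4.3) is headed "Predicted human plasma PK for 50 mg starting dose" and gives AUC to infinity of 3855 µg×h/mL and Cmax of 14.4 µg/mL, for IV administration.

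- One-compartment rate: k = Cmax/AUC = 14.4/3855 = 0.003735 per h.
- Half-life: ln 2/k = 0.693/0.003735 = 186 h, or 7.7 days.
- Time from dose to Day 14: 13 × 24 = 312 h.
- Tail fraction: exp(−0.003735 × 312) = exp(−1.165) = 0.31.

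Under linear PK, with Cmax read as the initial concentration after an IV bolus, 0.31 is a lower bound. Further compartments with the same Cmax and AUC can only raise the tail (Jensen's inequality), and SQ absorption moves exposure later. For assumed half-lives of 14 and 28 days, the one-compartment tail would be exp(−0.693 × 13/14) = 53% and exp(−0.693 × 13/28) = 72%.

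**Weight of one subject.** 1/7 = 14% of a CD388 dose group.

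**Chance that the rule is triggered.** The protocol gives no rate of Grade 3–4 rash. For assumed rates of 1%, 2% and 5%, the chance of at least one among 21 CD388 subjects is 1 − 0.99^21 = 19%, 1 − 0.98^21 = 35% and 1 − 0.95^21 = 66%.

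**The case against.** The strongest case on the other side has four parts.

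1. **The event may never occur, and not every subject is affected.** Section 4.1.2.2 reports only Grade 1 and 2 TEAEs in the first-in-human study. Appendix 4 ties its listed visits and assessments to causally related rash. Placebo samples are not analyzed (Section 6.1), so for 6 of the 27 subjects no PK or ADA data would be lost. This stands, and it makes the point conditional.

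2. **Much follow-up is kept.** Grade 3–4 rash has its own visits, weekly while it persists. Section 6.2.1 allows mechanism work, including ADA, for related AEs of Grade 2 or higher. Section 11.3.1 keeps later related SAEs reportable. A related Grade 4 AE or related SAE within 28 days also halts the study for review (Section 7.6). All true, but the mechanism work is discretionary, and none of this restores the serial samples or routine collection of new AEs.

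3. **Withdrawal spares a seriously ill volunteer further procedures.** That is a fair consideration, though the protocol does not give it as a reason. It does not need a compulsory rule: under Section 7.4.1 the subject may withdraw consent, and the investigator may withdraw the subject in the subject's interest.

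4. **The 31% is less firm than it looks.** If the predicted Cmax is an end-of-infusion value, the bound is not strict. ADA could also change clearance in just these subjects. A later early-discontinuation sample would extend the observed curve. These are valid limits on the figure, but the sample counts do not depend on it.

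That Appendix 5 asks only for drug discontinuation could suggest that withdrawal was never firmly intended. It leaves the site with two texts to choose between, which is a further reason to correct Appendix 4.

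**Conclusion.** The concern holds. For Grade 3–4 rash, mandatory withdrawal avoids no exposure and ends scheduled PK, ADA and safety follow-up selectively in the worst reactors, while Grade 2 subjects may stay.

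The size is conditional on a Grade 3–4 rash in a CD388 subject. Over assumed withdrawal days from 7 to 60, between 8 and 2 of 17 post-dose PK samples and between 6 and 2 of 6 post-dose ADA samples are replaced by one visit. For withdrawal after Day 14, about 31% or more of AUC to infinity would be extrapolated unless the early visit falls later. That rests on linear PK and on the protocol's IV prediction. The record of the rash itself is not lost. This should be corrected because the inconsistency is clear and the correction is cheap, even though the event may be rare.

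**What to change.** In Appendix 4, delete the study-withdrawal wording for Grade 3–4 rash and extend the Grade 2 Note to all grades. Subjects are not re-exposed but, if they consent, remain in all scheduled safety, PK and ADA follow-up to Day 120/165. Rash treatment and the rash visit schedule stay as they are. So do consent withdrawal and withdrawal on the investigator's judgment under Section 7.4.1. Appendix 4 would then agree with Appendix 5.

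The cost is appendix wording only, since the visits and samples are already scheduled.

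Two numbering slips can be corrected in the same edit, though neither bears on this point. Appendix 5 requires a Grade 3–4 visit on rash day 5 that Appendix 4 does not list. Footnote a of Appendix 5 counts from Day 0 although it is attached to rash day 1.
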